## TIME AND EVENTS SCHEDULE – SCREENING AND TREATMENT PHASE

Phase	Screening	Treatment ee,kk								Treatment Extension ee,kk						
Day (D)/Week (W)	<Day -56	D1 a	W1	W2	W4	W8	W12	W16	W20	W24	W28	W32	W36	W40	W44	W48
Study Procedure																
Screening/Administrative																
Informed consent form (ICF) b	X															
ICF for optional pharmacogenomic samples	X															
Demographics	X															
Medical and surgical history	X															
Inclusion/exclusion criteria c	X															
Liver biopsy or Fibroscan d	X															
Ultrasound e	X															
Clinical status	X	X f														
Follicle-stimulating hormone test (postmenopausal women only)	X															
Serum pregnancy test (women of childbearing potential only)	X															
Testing for hepatitis A, B, C, D, and E virus and HIV-1 and -2	X															
Serum immunoglobulin M (IgM) anti-HBc antibody test	X															
HBV genotype g	X															
Visit with overnight stay h		X					X									
Check for eligibility for extension phase									X ii	X ii,gg						
Study Treatment Administration																
Randomization		X														
Dispense study medication	X			X	X	X	X	X	X	X	X	X	X	X	X	X ii
Administer study medication i	X	X	X	X	X	X	X	X	X	X	X pp	X	X	X	X	X
Distribute diary j					X			X								
Collect diary j							X			X						

Phase	Screening	Treatment ee,kk										Treatment Extension ee,kk						
		Day (D)/Week (W)	<Day -56	D1 a	W1	W2	W4	W8	W12	W16	W20	W24	W28	W32	W36	W40	W44	W48
Study Procedure																		
Safety Evaluations																		
Complete physical examination k	X										X							
Symptom-directed physical examination l		X	X	X	X	X	X	X	X	X	X	X	X	X	X	X	X	
Vital signs m	X	X	X	X	X	X	X	X	X	X	X	X	X	X	X	X	X	
Triple 12-lead ECG n	X	X			X		X			X			X				X	
Clinical Laboratory Tests																		
Hematology	X	X	X	X	X	X	X	X	X	X	X	X	X	X	X	X	X	
Blood chemistry o,p	X	X	X	X	X	X	X	X	X	X	X	X	X	X	X	X	X	
Blood coagulation	X	X	X	X	X	X	X	X	X	X	X	X	X	X	X	X	X	
Urinalysis q	X	X	X	X	X	X	X	X	X	X	X	X	X	X	X	X	X	
Alpha-fetoprotein	X																	
Urine pregnancy test (women of childbearing potential only)		X	X	X	X	X	X	X	X	X	X	X	X	X	X	X	X	
Efficacy Evaluations																		
Fibroscan r			X									X					X	
HBV Virology																		
HBV DNA and HBV RNA j	X	X	X	X	X	X	X	X	X	X	X	X	X	X	X	X	X	
Viral genome sequencing s	X	X		X	X	X	X	X	X	X	X	X	X	X	X	X	X	
HBV Serology																		
Anti-HBs and anti-HBe	X	X										X					X	
HBsAg and HBeAg t (qualitative)	X	X										X					X	
HBsAg and HBeAg u (quantitative)	X	X	X	X	X	X	X	X	X	X	X	X	X	X	X	X	X	
HBcrAg j	X	X	X	X	X	X	X	X	X	X	X	X	X	X	X	X	X	
Exploratory serology v		X		X	X	X	X	X	X	X	X	X	X	X	X	X	X	

Phase	Screening	Treatment ee,kk										Treatment Extension ee,kk						
		Day (D)/Week (W)	<Day -56	D1 a	W1	W2	W4	W8	W12	W16	W20	W24	W28	W32	W36	W40	W44	W48
Study Procedure																		
Pharmacokinetics																		
Blood sampling for pharmacokinetics of JNJ-56136379 and/or NA (sparse) w		X nn	X	X	X	X	X	X nn	X	X	X	X	X	X	X	X	X	
Blood sampling for pharmacokinetics of JNJ-56136379 and/or NA (semi-rich) (selected sites only) x		X nn						X nn										
Urine collection for pharmacokinetics of JNJ-56136379 and/or NA (selected sites only) y		X z						X										
Blood sampling for exploratory pharmacokinetics of hormonal contraceptives and their metabolites (sparse, all women on hormonal contraceptives) dd,ii		X nn						X nn		X	X							
Blood sampling for exploratory pharmacokinetics of hormonal contraceptives and their metabolites (semi-rich, all women on hormonal contraceptives included in the PK subgroup) dd,mm		X nn						X nn										
Information on hormonal contraceptive cycle oo	X	X						X		X	X			X			X	
Exploratory Biomarkers																		
Host mRNA		X	X	X	X	X	X	X	X	X	X	X	X	X	X		X	
Serum proteins		X	X	X	X	X	X	X	X	X	X	X	X	X	X	X	X	
Immune cells (PBMCs) (selected sites only) aa		X			X		X			X			X				X	
Pharmacogenomics (DNA)																		
Exploratory host genotyping (optional) bb			X															
Patient-reported Outcome Evaluationscc																		
EQ-5D-5L			X			X					X							

Phase	Screening	Treatment ee,kk										Treatment Extension ee,kk				
Day (D)/Week (W)	<Day -56	D1 a	W1	W2	W4	W8	W12	W16	W20	W24	W28	W32	W36	W40	W44	W48
Study Procedure																
HBQOL		X			X						X					
MOS-CFS Cog-R		X			X						X					
SF-36v2		X			X						X					
Ongoing Participant Review																
Concomitant therapy	X	X	X	X	X	X	X	X	X	X	X	X	X	X	X	X
Adverse events	X	X	X	X	X	X	X	X	X	X	X	X	X	X	X	X

- a. Day 1 samples are to be collected before the first dose of study drugs.
- b. The ICF must be signed before the first study-related activity.
- c. Minimum criteria for the availability of documentation supporting the eligibility criteria are described in Section 17.4. Check clinical status again before first dose of study medication.
- d. Liver disease staging assessments will be performed by means of a liver biopsy or Fibroscan during the screening period in case not performed within 1 year (in case of liver biopsy) or 6 months (in case of Fibroscan) prior to screening.
- e. Subjects must have absence of signs of hepatocellular carcinoma (HCC) on an abdominal ultrasound performed within 2 months prior to screening or at the time of screening. In case of suspicious findings on conventional ultrasound the subject may still be eligible if HCC has been ruled out by a more specific imaging procedure (contrast enhanced ultrasound, computed tomography [CT] or magnetic resonance imaging [MRI]).
- f. If a subject's clinical status changes (including any available laboratory results or receipt of additional medical records) after screening but before the first dose of study drugs is given such that he or she no longer meets all eligibility criteria, then the subject should be excluded from (further) participation in the study.
- g. HBV genotype will be determined at screening using standard genotyping assay if HBV DNA levels are sufficiently high. In virologically suppressed subjects, available historical data on previous HBV genotype assessment will be collected in the eCRF. Exploratory genotyping assays might be performed.
- h. Only applicable to subjects undergoing semi-rich pharmacokinetic and 24-hour urine sampling (pharmacokinetic subgroup).
- i. Study drugs should be taken in the morning at approximately the same time each day, together with breakfast, except for ETV which should be taken on an empty stomach. At each study visit, the study drugs should be taken on site under the supervision of the study staff. The time of study drug intake should be recorded.
- j. A subject diary will be provided to the subjects in the pharmacokinetic subgroup, and female subjects using hormonal contraceptives (regardless of type and route of administration). These subjects should report the times of study drug intake at home for 1 week prior to their Week 12 and Week 24 visits in this diary.
- k. Complete physical examination, including height, body weight, temperature, skin examination, and other body systems.
- l. Symptom-directed physical examination, including body weight and temperature.
- m. Vital signs include supine systolic blood pressure (SBP), diastolic blood pressure (DBP), and pulse rate.
- n. If blood sampling or vital signs measurement is scheduled for the same time point as ECG recording, the procedures should preferably be performed in the following order: ECG(s), vital signs, blood draw.

- o. Biochemistry samples must be taken fasted for at least 10 hours for measurement of phosphorus, calcium, creatinine clearance, and lipids. Subjects should bring their study drug with them to each visit and have that day's intake at the site.
- p. Creatinine clearance (estimated by the estimated Glomerular Filtration Rate [eGFR], which is calculated by the Modification of Diet in Renal Disease [MDRD] formula) will be assessed.
- q. In case of a positive dipstick result, a urine sample will be set aside for additional examination of the positive parameter (eg, quantification as applicable).
- r. Only applicable to subjects in the pharmacokinetic subgroup and subjects enrolled at a site with an on-site Fibroscan device.
- s. Sequencing on Day 1 (predose) will be performed by default if HBV DNA levels are within the ranges required for the sequencing assay; other samples may be sequenced based on the sponsor virologist's request.
- t. In virologically suppressed subjects, available historical data on HBeAg status before start of NA treatment will be collected in the eCRF.
- u. Quantitative HBeAg assessment will only be performed in subjects who are defined HBeAg-positive at screening based on a qualitative HBeAg assay.
- v. Exploratory serology samples may be analyzed at the sponsor's discretion. Samples may be used to assess virologic or serologic markers of HBV.
- w. Sparse pharmacokinetic sampling will be performed for all subjects. One sample predose at all indicated time points (except on Day 1: one sample 2 hours postdose only). Study drug should be taken on site. The time of study drug intake will be recorded.
- x. Approximately 35% of all subjects (at selected sites only) will undergo semi-rich pharmacokinetic sampling (pharmacokinetic subgroup) predose and 2, 4, 12, and 24 hours postdose. The study drug should be taken on site. The time of study drug intake will be recorded.
- y. Approximately 35% of all subjects (at selected sites only) will have 24-hour urine sampling (pharmacokinetic subgroup) during the intervals 0-2, 2-12, and 12-24 hours postdose. This sampling schedule will require an overnight stay on site.
- z. Applicable to Treatment Arms 4-5 and 9-10 only.
  - aa. Immune cell samples (peripheral blood mononuclear cells [PBMC]) may be collected (selected sites only).
  - bb. The pharmacogenomic (DNA) sample should preferably be collected at baseline. This sample is optional and will only be collected from subjects who consent separately to this component of the study.
  - cc. PRO assessments will be performed by subjects at sites where appropriate translations are available. Subjects will complete the 5-level EuroQol 5-Dimension (EQ-5D-5L), Hepatitis B Quality of Life Instrument (HBQOL), Medical Outcomes Study Cognitive Functioning Scale-Revised (MOS-CFS Cog-R), and Short Form 36 version 2 (SF-36v2) on an electronic device during the specified study visits. The PRO assessments are preferably to be completed immediately after dosing.
  - dd. For women on stable ( $\geq 3$  months) hormonal contraceptive treatment at screening, as well as women starting hormonal contraceptive treatment during the study, in which case the first blood sampling should occur at the next scheduled visit (note: all hormonal contraceptives, regardless of type and route of administration).
  - ee. All study visits are to be scheduled relative to the baseline visit date and are to occur at the end of Weeks 1, 2, 4, 8, 12, 16, 20, 24, 28, 32, 36, 40, 44 and 48. The visit window is  $\pm 2$  days of the protocol-specified date at Weeks 1-4,  $\pm 5$  days of the protocol-specified date through Week 48.
  - ff. Eligibility to enter the treatment extension phase will be determined at Week 20 and Week 24 of the initial 24-week treatment phase, ie, subjects must have completed the initial 24 weeks of treatment and must have achieved a virologic response by Week 20 (HBV DNA  $<200$  IU/mL of the HBV DNA assay) without experiencing any safety concerns precluding continued study drug treatment as determined by the investigator.
  - gg. Subjects enrolled in the study before the Amendment 2 came into effect will need to consent separately for participation in the extension phase. Subjects choosing not to participate in the extension phase will complete their assigned 24-week treatment after which they will enter the 24-week follow-up period. Subjects who are enrolled after the Amendment 2 came into effect will consent to the possible treatment extension by signing the ICF at the start of the study.
  - hh. Dispensing of JNJ-56136379/placebo is only applicable for subjects who will enter the treatment extension phase. NA will be dispensed for subjects starting or continuing NA treatment in the treatment extension phase or the follow-up phase.
  - ii. Only applicable for subjects who do not meet the treatment completion criteria and start or continue NA treatment. No JNJ-56136379/placebo will be dispensed.
  - jj. HBcAg and HBV RNA samples may be batched and only selected samples may be tested. Samples can be used for assessment of other serologic/virologic markers of HBV.

- kk. Subjects who discontinue treatment early will have an early treatment withdrawal visit and will enter follow-up (see Schedule 1) unless they withdraw consent. Subjects who withdraw consent will be offered an optional safety follow-up visit.
- ll. Sparse pharmacokinetic sampling will be performed for all female subjects on hormonal contraceptive treatment (regardless of type and route of administration). One sample predose on Day 1 and one sample at 1 hour postdose at all other indicated time points (also refer to footnote nn). On sampling days, female subjects on oral hormonal contraceptive treatment should take their contraceptive treatment as usual, and time of intake will be recorded.
- mm. All female subjects that are on a hormonal contraceptive treatment (regardless of type and route of administration) and that are included in the PK subgroup will undergo semi-rich pharmacokinetic sampling predose and at 2, 4, 12, and 24 hours postdose. The oral contraceptive treatment should be taken as usual, and time of intake will be recorded.
- nn. For subjects who are included in the PK subgroup (ie, those who undergo semi-rich sampling), only the sample for the semi-rich sampling set needs to be taken on Day 1 and Week 12 (no sparse sampling on these days and time points).
- oo. For female subjects on a hormonal contraceptive regimen (regardless of type and route of administration), the start of contraceptive administration at the last initiated cycle (if applicable for the type of contraception) will be documented in the eCRF.
- pp. Subjects in the JNJ-56136379 250 mg monotherapy arm (Treatment Arm 6) who meet the treatment extension criteria (see Section 6.1), will receive JNJ-56136379 in combination with NA treatment from Week 24 to Week 48.

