## **Safety Analyses**

The population for the safety analysis will consist of all subjects who received at least one dose of study drug. Baseline is defined as the last assessment prior to the first study drug administration.

The incidence of AEs will be summarized by body system and preferred term for each study treatment. Actual values and changes from baseline in clinical laboratory values, vital signs, and ECG parameters will be presented descriptively (n, mean, SD, median, minimum, maximum). The percentage of subjects with abnormal clinical laboratory findings, vital signs, and ECG parameters will be presented by study treatment and study phase. Physical examination findings and changes from baseline will be summarized.

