- Treatment with JNJ-56136379 and placebo will be stopped at Week 24 in all subjects who are not eligible to continue treatment in the extension phase, at Week 48 in subjects who continued treatment in the extension phase, and at time of discontinuation in all subjects who discontinue treatment early (24- or 48-week treatment). NA treatment (either ETV or TDF as per local practice) should be continued or, in case of JNJ-56136379 monotherapy during the 24-week treatment phase, started at Week 24 as per local treatment guidelines. An additional 24-week follow-up (as per local treatment guidelines), by their primary care physician outside of the study, is recommended after the 24-week follow-up phase in the study, for subjects who do not continue or start NA treatment at Week 24.
- Complete physical examination, including body weight, temperature, and skin examination.
- Symptom-directed physical examination, including body weight and temperature.
- Vital signs include supine SBP, DBP, and pulse rate.
- If blood sampling or vital signs measurement is scheduled for the same time point as ECG recording, the procedures should preferably be performed in the following order: ECG(s), vital signs, blood draw.
- Biochemistry samples must be taken fasted for at least 10 hours for measurement of phosphorus, calcium, creatinine clearance, and lipids.
- Creatinine clearance (estimated by the eGFR, which is calculated by the MDRD formula) will be assessed.
- Samples may be sequenced based on the sponsor virologist's request.
- Quantitative HBeAg assessment will only be performed in subjects who are defined HBeAg-positive at screening based on a qualitative HBeAg assay.
- Exploratory serology samples may be analyzed at the sponsor's discretion. Samples may be used to assess virologic or serologic markers of HBV.
- One sample at any time during the visit.

- l. Immune cell samples (PBMC) may be collected (selected sites only).
- m. PRO assessments will be performed by subjects at sites where appropriate translations are available. Subjects will complete the EQ-5D-5L, HQQOL, MOS-CFS Cog-R, and SF-36v2 questionnaires on an electronic device during the specified study visits. The PRO assessments are preferably to be completed before any tests, procedures or other consultations for that visit to prevent influencing the subject's perceptions.

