- q. For female subjects on a hormonal contraceptive regimen (regardless of type and route of administration), the start of contraceptive administration at the last initiated cycle (if applicable for the type of contraception) will be documented in the eCRF.
- r. PRO assessments will be performed by subjects at sites where appropriate translations are available. Subjects will complete the EQ-5D-5L, HQQOL, MOS-CFS Cog-R, and SF-36v2 questionnaires on an electronic device during the specified study visits. The PRO assessments are preferably to be completed before any tests, procedures or other consultations for that visit to prevent influencing the subject's perceptions.

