## **2.2. Definition of Baseline**

The last observed measurement before the date and time of the first administration of the study agent will be considered the baseline measurement.

In case the first administration time and/or the measurement time is missing, the day 1 measurement will be considered as baseline measurement. The underlying assumption is that the protocol is followed which states that day 1 samples are to be collected before the first dose of study drugs.

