### **8.5. PRO Analysis Methods**

#### **8.5.1 Baseline**

The Day 1 ePRO data have been recorded few minutes after first administration dose, as these time differences between dose administration (Day1) and ePRO data collection on Day 1 are very small and in order to have baseline values for all subjects with ePRO data on Day 1, ePRO baseline is defined as values before or on the date of the first administration dose (Day1).

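### PROs are completed after dosing at treatment visits, including Day 1, but before any procedure at follow-up, so the baseline in open-label Arms 1 and 6 follows disclosure and changes to follow-up mix two conditions

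*Protocol*

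**What the plan says.** Footnote cc of the protocol's Time and Events Schedule for the screening and treatment phase, repeated in SAP Appendix 5, governs PROs at Day 1 and later treatment visits: "The PRO assessments are preferably to be completed immediately after dosing". Footnote m of follow-up Schedule 1, which also covers the early treatment withdrawal visit, gives a different order and a reason: "The PRO assessments are preferably to be completed before any tests, procedures or other consultations for that visit to prevent influencing the subject's perceptions". Schedule 2, footnote r, says the same. Protocol Section 9.8 describes how the questionnaires are administered but sets no timing that would reconcile the two rules.

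SAP 2.2 sets the general baseline: "The last observed measurement before the date and time of the first administration of the study agent will be considered the baseline measurement". SAP 8.5.1 makes an exception for PROs. It reports that "The Day 1 ePRO data have been recorded few minutes after first administration dose", calls the gap very small, and counts any value dated on or before the first dosing date as baseline.

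Randomisation is on Day 1 (protocol Section 9.1.3). Arms 1 and 6 are open-label (Section 5). Subjects in the other arms stay blinded to JNJ-56136379 versus placebo until the end of the study (Section 11.11).

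**The concern.** The protocol names a risk, that what happens at a visit may colour the answers, and guards against it at follow-up. On Day 1, where every change score starts, it asks for the reverse order. By then the subject has been randomised and dosed and will normally have had the pre-dose work: footnote a requires that "Day 1 samples are to be collected before the first dose of study drugs", and footnote n puts ECG and vital signs ahead of the blood draw.

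SAP 8.5.1 defends the post-dose baseline by the few minutes since dosing. That answers a concern about drug effect. It does not address subjects who have just learned that they will receive JNJ-56136379 without an NA, or the fact that follow-up scores are collected under another instruction.

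At stake are the PRO contrasts involving monotherapy and any reading of PRO change after treatment ends. SAP 8.5.2 takes change from baseline into descriptive summaries, clinically important change, cumulative distributions and a mixed model. The model's fixed effects are treatment, time and their interaction, so nothing in it deals with a baseline measured after disclosure.

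**Working it through.** The plan states no figure for this issue, so there is none to reproduce. The check is a count of subjects and a comparison of conditions.

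**Who knows the assignment at the PRO baseline?** Inputs from protocol Section 3.1: per part, 70 currently untreated subjects randomised 3:1:3 (30 open-label, 10, 30) and 40 virologically suppressed subjects randomised 1:3 (10, 30); two parts.

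- Planned total: 2 × (70 + 40) = 220.
- Open-label monotherapy: 2 × 30 = 60.
- Share of all subjects: 60/220 = 27%.
- Share of currently untreated: 60/(2 × 70) = 60/140 = 43%.
- Share of virologically suppressed: 0/(2 × 40) = 0/80 = 0%.

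The other 140 − 60 = 80 untreated subjects can tell only that they are not in a monotherapy arm.

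**Which changes compare unlike conditions?**

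| Change from Day 1 to | Baseline rule | Later rule | Same? |
|---|---|---|---|
| Treatment visit | after dosing (cc) | after dosing (cc) | yes |
| Early withdrawal visit | after dosing (cc) | before procedures (m) | no |
| Follow-up visit | after dosing (cc) | before procedures (m or r) | no |

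End of treatment can fall in either row. SAP 2.3 takes it as the last visit in the treatment phase, which for subjects who do not enter the extension or who stop early runs to 5 days after the last intake. It can therefore be a scheduled treatment visit for one subject and an early-withdrawal visit for another.

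**When does a post-disclosure baseline bias a contrast?** Let d1 be the mean shift in score on Day 1 caused by knowing the open-label assignment, relative to the comparator arm, and dt the same shift at a later visit. Relative to the contrast without that knowledge, the bias is:

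- change from the post-disclosure baseline: dt − d1;
- change from a pre-disclosure baseline: dt;
- actual scores at the visit: dt.

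If the reaction fades (dt = 0), the planned change score is biased by −d1 and the other two are unbiased. If it persists unchanged (dt = d1), it cancels from the planned change score and remains in the other two. The planned analysis is thus vulnerable to a transient reaction. Neither d1 nor dt can be obtained from the documents.

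**Which instruments are exposed?** EQ-5D-5L asks about health today and is the most open to a momentary reaction. SF-36v2 (protocol Section 9.8 and Attachment 7) and MOS-CFS Cog-R (Attachment 6) use a four-week recall and are less so.

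**The case against.** Both instructions are preferences, so actual timing may vary. PROs are exploratory, no formal hypothesis testing is planned, and no primary or secondary objective depends on them. SAP 8.5.1 discloses the post-dose baseline and gives a reason. All of this stands and limits the weight of the point. It does not supply an answer on open-label knowledge or on the change of instruction.

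A reader might infer more than the documents support:

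- *That all PRO comparisons start from a baseline taken after assignment is known.* This is true only of Arms 1 and 6. JNJ-56136379+NA versus placebo+NA remains blinded and is not exposed by this route.
- *That all PRO changes mix two conditions.* Changes to treatment visits use one instruction at both ends. At follow-up the switch applies in every arm, so it does not by itself bias a between-arm contrast. It may be less even at end of treatment or early withdrawal, because Arm 1 was stopped early under Amendment 4; the number affected is not given, and footnote n waives some repeat PROs.
- *That the Day 1 PRO cannot count as a baseline because "Baseline is defined as the last assessment prior to the first study drug administration".* That sentence belongs to the protocol's safety analyses. The general rule is SAP 2.2, to which SAP 8.5.1 makes an express exception.
- *That every planned PRO result depends on the Day 1 value.* Protocol Section 11.9 plans mean scores over time, and SAP 8.5.2 plans actual values and response frequencies by visit.
- *That the bias is a definable fraction of the SAP's 5-point or 10-point thresholds.* Any such figure would only restate an assumed Day 1 shift.

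The strongest objection is to the obvious remedy. Changing footnote cc for everyone would leave subjects already enrolled with a post-dose baseline and pre-procedure later visits, bringing mixed conditions into the treatment phase, where timing is now consistent. That stands, and the fix needs a transition rule.

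**Conclusion.** The point holds within limits. The PRO baseline follows randomisation and first dose in every arm. In the open-label arms, 60 of 220 planned subjects and 60 of the 140 currently untreated, it also follows disclosure. Monotherapy change-from-baseline contrasts are therefore open to bias if the reaction on Day 1 is transient, mainly for EQ-5D-5L. Separately, changes from baseline to follow-up or early withdrawal compare scores collected under two instructions.

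The conclusion assumes that sites broadly followed the stated preferences; for Day 1, SAP 8.5.1 confirms post-dose collection. The size and direction of any bias are unknown. With exploratory endpoints this is a modest point, worth acting on because the correction is cheap and uses the protocol's own reasoning.

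**What to change.** **Protocol, footnote cc, and SAP Appendix 5.** For newly enrolled subjects, replace the last sentence with the follow-up rule: PROs come before any test, procedure, consultation or dosing, and on Day 1 before the assignment is disclosed. Arm 1 is fully recruited, so this cannot help there.

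**Transition rule.** Subjects whose Day 1 PRO was taken after dosing keep post-dose timing at their remaining treatment visits, so that conditions stay constant within subject. Flag the two timing cohorts in the data.

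**SAP 8.5.** State that changes to follow-up and early-withdrawal visits were collected under a different instruction from the Day 1 baseline. For contrasts involving Arms 1 and 6, add a sensitivity comparison of actual on-treatment PRO scores beside the change-from-baseline analysis. It should not replace that analysis: actual scores lose the adjustment for baseline and still carry any lasting effect of open-label knowledge, and some on-treatment scores in Arm 1 may be missing because the arm was stopped.

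**Cost.** One footnote with its transition rule, a data flag, one SAP statement and one sensitivity table. No visit, procedure or questionnaire is added. The downside is two timing cohorts to track.
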